- **Specific Aim #1 (Biochemistry): Determine if EAA elevates basal rates of muscle protein synthesis by up-regulating anabolic pathways & cyto-protective proteins, and inactivating catabolic pathways in the short-term vs. Placebo.**

Identifying molecular pathways that are up-regulated by EAA are needed in order to uncover potential mechanisms of action. Successful completion of the proposed research will determine the degree to which EAA elevate basal rates of muscle protein synthesis and the extent to which these changes coincide with increases in anabolic (SLC36A2, IGF-I, & VEGF) and cyto-protective (ATF4 & REDD1) pathways. As well, completion of Aim 1 will allow us to determine changes in muscle protein breakdown in parallel with changes in catabolic (FoxO3a) proteins (Fig. 3). We expect these findings will provide mechanistic data on the effects of EAA on muscle cell metabolism and signaling that will help explain how muscle atrophy is prevented and functional mobility accelerated following TKA.

To accomplish Specific Aim #1, subjects will be enrolled pre-operatively and asked to participate in a number of study-related activities designed to isolate the effect of EAA supplementation on muscle protein synthesis. Subjects will consume “heavy water” to aid in quantifying chronic muscle protein synthesis rates while consuming the study EAA supplement. Study specific blood draws, muscle imaging (via MRI) and muscle biopsies will be assessed at regular intervals. Patients will capture accelerometer data and complete three-day food diaries, as well as patient reported outcome measures designed to capture health-related quality of life, knee-specific functioning, pain and the degree to which the patient has an ability engage in total joint pre- and post-operative care. Finally, functional testing will capture patient strength and functional capabilities pre- and post-operatively.

The proposed research design will answer the following questions:

- 1.1 *Does EAA elevate or alter levels of muscle protein synthesis vs. Placebo?*
- 1.2 *Does EAA decrease or alter levels of muscle protein breakdown vs. Placebo?*
- 1.3 *Will EAA inactivate catabolic (FoxO3a) and up-regulate anabolic (SLC36A2, IGF-I, ATF4 and REDD1) pathways vs. Placebo?*
- 1.4 *Does inhibition of angiogenic factors (IFG-1 & VEGF) inhibit a pro-angiogenic response?*
- 1.5 *Does EAA influence markers of inflammation vs. Placebo?*

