Gene Expression: RNA will be extracted from 15-20 mg of muscle tissue according to protocol (Molecular Research Center, Inc, Cincinnati, OH). High quality RNA will be determined using lab-on-chip microfluidic technology automated nucleic acid electrophoresis and analysis. Total RNA will be reverse transcribed into cDNA using the iScript cDNA Synthesis Kit (Bio Rad, Hercules, CA) on a C1000 Thermal Cycler (Bio Rad, Hercules, CA). Determination of relative mRNA expression will be performed using a CFX96 Real-Time System coupled to a C1000 Thermal Cycler (Bio Rad, Hercules, CA) and Genomics Core facility NextSeq 500 at the University of Oregon.

Mitochondrial respiration. Oxidative phosphorylation rates in response to 50 μ M ADP will be determined in saponin permeabilized vastus lateralis biopsies (5-10 mg) using the two-channel high resolution respirometer (Oroboros Oxygraph; Innsbruck, Austria) with the saturating concentrations of the following substrate combinations [in mM]: pyruvate [5] + malate [5], palmitoylcarnitine [0.04] + malate [5], succinate [10] + 100 nM rotenone, or malate [5] + glutamate [10]. Respiration studies were performed at an initial oxygen concentration of 300 μ M at 37°C in MiR06 respiration buffer containing [in mM] EGTA [0.5], MgCl₂·6 H₂O [3], K-lactobionate [60], taurine [20], KH₂PO₄ [10], HEPES [20], sucrose [110], 1g/L BSA, 280U/ml catalase, pH 7.4 [with KOH].

Mitochondrial dysfunction may introduce sample bias as well as negatively impact short and longer-term function. To account for this, we propose to measure mitochondrial respiration using the Oroboros O2k respirometer, and normalize results statistically and use the non-operative leg as internal control.

Secondary Outcome Measures. Study Aim #1 will allow the team to collect preliminary functional outcome data to better inform the long-term study (Aim #2). The secondary outcome measures will be quantified using the following study activities and procedures:

- **Muscle volume.** The MRI unit is located at the Lewis Center for Neuroimaging (LCNI) on the University of Oregon campus. Should the MRI unit at LCNI be unavailable within study-specific assessment points (i.e. scheduling or mechanical issues), the MRI at the Slocum Center for Orthopedics will be utilized. In addition, patients in partnership with the study team, may elect to have all scans performed at the Slocum Center.

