Patient history, body composition, strength and functional data, blood samples, and muscle & fat tissue samples will be obtained specifically for research purposes. Coded data will be stored on computers that are password protected and in locked offices. Data on paper will be stored in files in a locked file cabinet (printouts) and computers in a key-code-access-only lab in a badge-access building. All data and material collected will be coded. Codes linked to subjects' names will be stored in the PI's office (key lock) on a MacPro with password protection and backed up to a protected and locked time capsule 2T external storage device. All MR images will be transferred as DICOM files to [name] laboratory via encrypted electronic data transfer protocol currently established by the collective efforts of our IT department at the University of Oregon.

All research personnel will have access to the coded data, and coded blood and coded tissue specimens. Only the PI, physicians, and study coordinators will have access to the identifiable private information. Only the study coordinator will have access to patient coding.

Please see **Data Elements Table** (Appendix 1) for a list of all elements needed to complete the aims of this trial.

Data Analysis.

[name], will be responsible for the statistical analysis of this project. He will be responsible for the statistical modeling and, along with [name], MA, will analyze all data points in our study (Oregon Research Institute).

- **Aim #1:** Aim 1 will compare differences between the two groups (EAA vs. Placebo) across experimental conditions in the change in post-TKA metabolism (synthesis & breakdown) from baseline to 1 and 2 wk post-TKA.
- **Aim #2 (trials 1 & 2):** Aim 2 will also compare measures of functional mobility with muscle cell structure (CSA) and mitochondrial function (respiration), including accelerometer and quality of life measures.

Analysis of covariance. ANCOVA will be used to answer research questions for aim 1 & 2. ANCOVA maximizes statistical power by incorporating the pretest measure as a regression-based control, reducing individual variance. Power improves as the pre-post correlations increases. Our preliminary data indicate that pre-post correlations for many key endpoints are highly correlated (e.g., muscle volume $r = .96$ for operative leg and $r = .97$ for non-operative leg; strength $r = .42$ to $.89$; stair-climb down time $r = .78$).

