Power analyses. For our power calculations, we have assumed a Type I error rate (α) of $.05$, two-tailed. We based power calculations on effect sizes (d) that we derived from analysis of preliminary data preliminary data and prior studies (10, 30, 32, 33, 36, 41, 51, 113). We calculated d as the standardized mean difference between treatment conditions at follow-up: $d = (x_C - x_T)/S$, where x_C represents the primary outcome mean in the Placebo and EAA conditions and S is the pooled standard deviation, after adjusting x for pretest scores and covariates (sex, tourniquet time, age, body mass index, fat/carbohydrate/protein intake).

We propose to enroll **40 total subjects for Aim 1** who are retained through protocol completion (20/group, EAA and Placebo, randomized to either 1 week or 2 week post-operative biopsies), and **80 total subjects** (40/group, EAA and Placebo) **for Aim 2** who are retained through protocol completion to account for possible attrition and to ensure sufficient power to test the hypotheses that EAA therapy up-regulates basal levels of muscle protein synthesis, and reduces post-operative atrophy bilaterally, preserves quadriceps strength, and improves functional mobility relative to a Placebo condition.

Effect sizes. Effect sizes were as follows: (a) Cell and FSR data: REDD1 $d = 1.24$, SLC36A2 $d = 1.27$, and FSR $d = 1.51$ (FSR calculated from mean change from baseline). The mean effect across outcomes was $d = 1.37$, reflecting large effects. (b) Physiological and functional data (percent change from Baseline to 6 wk): operative quadriceps volume $d = 1.52$, and isometric strength $d = .90$; non-operative quadriceps volume $d = 1.05$, and isometric strength $d = .66$; timed up-and-go test $d = 1.03$, timed stair ascent $d = 1.08$, timed stair descent $d = 1.13$, and six-minute walk test $d = .70$. Mean effect size was $d = 1.01$, reflecting large effects.

Power calculations. Power calculations were based on the sample size and minimally detectable ES (MDES) as follows:

- **Aim #1:** For a sample size of 20 completed subjects/group (10/group for metabolic studies, however, EAA vs. Placebo = 20 total EAA and 20 total Placebo). Aim 1, proposed study can detect

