ESs of $d > 1.10$ with 85% power, assuming no pretest covariate, and the minimally detectable ES drops to 0.95 or 0.72 with pretest covariates of $r = .50$ or $.75$, respectively. The preliminary results show ESs averaged 1.37 for Cell and FSR outcomes, and all exceeded .95. The proposed study would thus have the power to detect anticipated condition effects for Cell and FSR outcomes in Aim 1 with 10 subjects per condition. We can also detect moderation effects for sex if the associated interaction accounts for at least 21% to 31% of the variance, assuming covariate of $r = .75$ or $.50$, respectively.

- **Aim #2:** For a sample size of 40 completed subjects/group (EAA and Placebo), the proposed study can detect ESs of $d > .79$ with 85% power, and the minimally detectable ES drops to .68 or .52 with pretest covariates of $r = .50$ or $.75$, respectively. Preliminary results show an average ES of $d = 1.01$ across all Aim 2 outcomes, so this study will have power to detect anticipated physiological and functional effects with 40 subjects per condition. We can detect condition-by-sex moderation effects if the associated interaction accounts for at least 12% to 19% of the variance, assuming covariate of $r = .75$ or $.50$, respectively. The tests of sex-by-condition interactions in both aims are likely underpowered for some important effects, so we will also consider the size of the effect, even if not statistically significant, as an indicator of potentially important sex-related differences.

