Potential Research Benefits to Participants

The proposed research is based on strong preliminary evidence that EAA reduce post-operative muscle atrophy by 3-fold in the operative and non-operative lower extremities. Further in our pilot studies,

these positive results extended to gains in strength in the non-operative quadriceps—important for long-term ability to normalize function, and to accelerated recovery of functional mobility (stair descent). These data are all derived from older adults. Preserving quadriceps strength is clinically important because poor strength is directly linked to reduced physical function and gait. Quadriceps weakness inhibits balance (84), reduces functional mobility (20, 82), and increases the risk of falls (83) in older adults. Our preliminary data suggest that patients on EAA treatment lost less muscle from their extremities compared to subjects on placebo. An additional potential benefit will be our potential to provide physical therapy to patients without insurance or in instances where the subjects insurance does not pay for the total number of visits we require for this study. These may be considered a potential benefit.

We repeated this study with 39 patients in 2014-2016 and again found the group taking EAA lost less muscle than the placebo group.

Investigator Experience

University of Oregon

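### Aim 1 fixes no deciding outcome, leg and biopsy week and states no multiplicity control, so its false-positive risk is about 15–18% for synthesis alone and 23–34% for synthesis and breakdown

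*Combined protocol and SAP*

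**What the plan says.** The Aim #1 bullet under Data Analysis compares EAA with Placebo "across experimental conditions in the change in post-TKA metabolism (synthesis & breakdown) from baseline to 1 and 2 wk post-TKA". That sentence covers two outcomes, synthesis and breakdown, at two post-operative times.

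Other parts of the plan go wider:

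- Primary Biochemical Outcome Measures lists D₂O-based synthesis and breakdown, fibre cross-sectional area (CSA), extracellular matrix, inflammatory infiltration, mitochondrial respiration under four substrate combinations, Western blots and gene expression. All sit under the same primary label.
- The Specific Aims pose questions 1.1 to 1.8 without ranking them. Question 1.3 asks "Will EAA inactivate catabolic (FoxO3a) and up-regulate anabolic (SLC36A2, IGF-I, ATF4 and REDD1) pathways vs. Placebo". The Hypothesis section also names VEGF, which makes six signalling targets.
- Randomization Assignments for Aim 1 lists the data to be collapsed over biopsy week (questionnaires, activity, food log, strength, muscle volume, function). Metabolism is to be examined at 1 and 2 weeks and between legs.
- CSA and respiration are to be expressed relative to the non-operative leg.
- ANCOVA is the method for all research questions. On error control, Power analyses says only "we have assumed a Type I error rate (α) of $.05$, two-tailed".
- The effect-size definition uses a term that "represents the primary outcome mean in the Placebo and EAA conditions", but no Aim 1 outcome is singled out as that primary outcome.

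I found no hierarchy, alpha split or false-discovery-rate (FDR) rule for Aim 1.

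**The concern.** Aim 1 has its own randomised patients and its own outcomes, and its results must be reported to the FDA under the IND. If several contrasts have equal standing and each is tested at .05, the chance that at least one is significant with no true effect is well above .05. Contrasts can also disagree: synthesis might differ in one leg at one week and not elsewhere, and the plan does not say which result answers question 1.1. A reader of the eventual report could not tell a planned answer from the most favourable of several.

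**Working it through.** **Inputs from the documents.** Two-sided α = .05 per test and 1:1 allocation (Study Design, Power analyses). Sample size: "For a sample size of 20 completed subjects/group (10/group for metabolic studies", so 10 per arm at each biopsy week, or 20 per arm if weeks are pooled. Two legs. Two weeks, with different patients in each, so the weeks are independent.

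**Inputs I have to assume.** Correlation between outcomes from 0 to 0.8 and between legs from 0 to 0.8. The documents give neither.

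**The plan's own figure.** There is no family-wise error rate to reproduce. The nearest stated figure is the Aim 1 detectable effect, "ESs of $d > 1.10$ with 85% power, assuming no pretest covariate". A two-sample t-test gives a detectable d of 0.97 at 20 per group and 1.42 at 10 per group, so 1.10 matches neither. It matches 16 per group (1.095), a size the plan does not state. This does not enter the error rates below, which are computed with no effect present. It matters for the fix, because 1.42 exceeds the plan's mean anticipated effect of 1.37.

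**Counting the contrasts.**

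- Synthesis alone: 1 × 2 legs × 2 weeks = 4.
- Synthesis and breakdown (the analysis sentence): 2 × 2 × 2 = 8.
- Synthesis plus FoxO3a, SLC36A2, IGF-I, VEGF, ATF4 and REDD1: 7 × 2 × 2 = 28. Questions 1.1 to 1.3 (synthesis, breakdown and five proteins) also give 7 × 2 × 2 = 28. The plan states no count.

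**Formulas.** For m independent tests, the chance of at least one significant result is 1 − 0.95^m, and the chance of at least one in a given direction is 1 − 0.975^m.

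- m = 4: 1 − 0.95⁴ = 18.5%; one direction 9.6%.
- m = 8: 1 − 0.95⁸ = 33.7%; one direction 18.3%.
- m = 28: 1 − 0.95²⁸ = 76.2%; one direction 50.8%.

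Correlated tests were handled by simulation under the global null.

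| Contrasts | Tests | Any direction, independent | Any direction, correlated | One direction, independent | One direction, correlated |
|---|---|---|---|---|---|
| Synthesis | 4 | 18.5% | 15–18% | 9.6% | 8–9% |
| Synthesis, breakdown | 8 | 33.7% | 23–32% | 18.3% | 12–17% |
| Synthesis, six targets | 28 | 76.2% | 41–74% | 50.8% | 26–41%* |

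*Outcome correlation 0.3 to 0.7, leg correlation 0.5 to 0.7.

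For 28 tests in any direction, the rate is 63% with both correlations at 0.5 and about 41% at the high-correlation end.

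**If weeks are pooled (20 per arm).** Synthesis in two legs gives about 9% (1 − 0.95² = 9.75% if independent). Seven outcomes in two legs (14 tests) give 23–49% when correlated and 51.2% if independent.

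**The case against.** The strongest reply is that the plan is narrower than its list of measures. The Aim 1 analysis sentence names only synthesis and breakdown. The aim title, the hypothesis and the power section all lead with synthesis, and the hypothesis is that EAA raises synthesis through the signalling pathways. The markers then explain a synthesis effect and are not substitutes for it. A reader might infer that any one positive marker, in either leg at either week, would establish the Aim 1 claim. The hypothesis as worded does not support that. This part of the reply stands, and it is why the 4-test and 8-test figures lead here.

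It does not remove the problem. Synthesis alone still has four contrasts and no rule for choosing among them. Question 1.3 is posed in its own right, and the power section claims power for cell outcomes as well as for fractional synthesis rate (FSR), so tests of the markers are planned.

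A reader might also infer a primary family of up to 56 tests and a false finding that is more likely than not. Fourteen outcomes × 2 legs × 2 weeks does equal 56. But CSA and the four respiration states are taken relative to the non-operative leg, so leg does not double them: 9 × 2 × 2 + 5 × 2 = 46. Nor does the plan say that each substrate combination is a separate test. Even for 28 tests, the rate falls below one half at high correlation. With 14 pooled-week tests the correlated range stays below one half. For a false result in one direction, only 28 fully independent tests exceed it, at 50.8%.

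Two smaller points also stand. The Aim 1 functional data are already described as preliminary input to Aim 2. And the statement under Potential Research Benefits that the investigators "again found the group taking EAA lost less muscle than the placebo group" concerns muscle loss, a secondary outcome. It gives no p-value and does not name Aim 1, so it is not evidence of selective reporting of the biochemistry.

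**Conclusion.** The omission is real. No outcome, leg and biopsy week (or pooled-week contrast) is designated as deciding Aim 1, and nothing limits the error across the contrasts. With no true effect, the chance of at least one false positive is three to almost seven times the nominal .05 on the plan's narrow readings: about 15–18% for synthesis alone and 23–34% for synthesis and breakdown. It is about 41–76% if synthesis and the six named targets are all tested in both legs at both weeks. These figures rest on assumed correlations, a global null, separate analysis of the two weeks and, for the last range, my own count of tests. The documents do not support a general statement that a false mechanistic finding is more likely than not.

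**What to change.** What to change depends on whether Aim 1 has been unblinded. The recruitment text for Aim 2 says the first part was completed in 2016. Potential Research Benefits reports group results from 39 patients studied in 2014–2016. Both suggest that it has, and the sponsor should state which case applies.

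- **If Aim 1 is still blinded and unanalysed:** in the Aim #1 part of Data Analysis, name one synthesis contrast at two-sided .05. One option is the operative leg, EAA versus Placebo, with 1- and 2-week patients combined and biopsy week as a factor. Test the other leg only if the first is significant. Treat all other comparisons as exploratory, with 95% confidence intervals and FDR control within the signalling and gene family.
- **If Aim 1 has been unblinded:** do not name a primary after the fact. Report all Aim 1 comparisons as exploratory, with the number of tests performed, estimates with 95% confidence intervals, and Holm- or FDR-adjusted p-values.

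The cost is wording and reporting labels, with no new data. The downside is that a single unadjusted positive marker can no longer be called confirmatory.

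In the blinded case, one named contrast costs little power. At the plan's FSR effect of d = 1.51 with no covariate, power is 89% with 10 per group and 99.6% with 20 per group. Keeping every contrast co-primary under Bonferroni at 10 per group would cut this to 62% for 8 tests and 42% for 28.

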Prospective, randomized, blinded, controlled, two-arm, parallel clinical trial design with 1:1 allocation ratio to EAA versus Placebo. Staged enrollment is planned; we will complete Aim #1 before enrolling into Aim #2.

Investigational Supplement.

This trial is being conducted under IND#121601, with mandates to report results from Aim #1 to the Food and Drug Administration (FDA). The investigational supplement (or Placebo) will be ingested twice-daily, at 10:00a and 2:00p for one week prior to TKA surgery.

- Aim 1 -Supplement will be compounded by Northwest Compounds, and ordered per standard of care for pharmaceutical ordering (fax or phone call) and dispensing.
- Aim 2 – Supplement will be supplied by MEND Nutrition, Inc. Supplement will come individual containers shipped directly to the [name] Lab. Containers will be distributed to patients by study coordinators. Patient will measure two (2) scoops per dose (twice daily). Scoop provided in each container.

Aim 1 Supplement will be suspended on the day of surgery and resume on post-operative day #1. On post-operative days where subject participates in physical therapy, supplementation will occur within one hour of treatment (20 g of EAA or Placebo). The EAA supplement or Placebo composition is described in Table 1 below. Our preliminary study suggest the EAA supplementation is safe and no subjects withdrew due to problems with supplement ingestion (37).

Aim 2 Supplement will be suspended on the day of surgery and resume on post-operative day #1. On post-operative days where subject participates in physical therapy, supplementation will occur within one hour of treatment (23.42 g of EAA or Placebo). The EAA supplement or Placebo composition provided by MEND Nutrition, Inc. is described in Table 2 below. Our preliminary study suggest the EAA supplementation is safe and no subjects withdrew due to problems with supplement ingestion (37). Supplement composition has changed due to new manufacturer/supplier of the supplement (MEND). To our knowledge there are no scientific or risk implications related to the change in proportions.

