Randomization Assignments. Aim #1 will consist of 2 groups (N=20/group through protocol completion; EAA vs. Placebo) that are identical in protocol design except for metabolic studies.

Metabolic studies will partition the EAA group into 2 (post-TKA bilateral biopsy at 1 or 2 weeks after

UO IRB Protocol #12272013.024 PeaceHealth Protocol #551187

January 2019

Research
 Compliance Services
 Page | 11
 01/26/2019-11/06/2019

"APPROVED"

surgery) and Placebo group into 2 (post-TKA bilateral biopsy at 1 or 2 weeks after surgery). This will allow us to collapse data by group treatment group; questionnaire, activity, food-log, strength & activation, muscle volume and functional data (this equals N of 20 through protocol completion for EAA and N of 20 for Placebo through protocol completion; 20/group, enough for sex comparison), while enabling us to quantify changes over time in metabolism (D_2O) and at discrete time points after surgery (1 and 2 weeks post) between legs when 80% or more of muscle atrophy is occurring (37).

Primary Biochemical Outcome Measures.

To answer our study questions will be answered using an in vivo experimental design. **The procedure schedule can be referenced in Figure 1 (page 17, following a description of all study-related procedures and measures for Aim #1).**

Deuterium Oxide Ingestion Followed by Muscle Biopsies. Deuterium oxide (D_2O , i.e., heavy water) will be used to quantify chronic (days) muscle protein synthesis rates. D_2O will be ingested (50 ml) three times per day for 7 days leading up to TKA. During TKA surgery, a single biopsy will be obtained in the OR from each leg. Beginning on POD#1 and continuing through week 1 or week 2, subjects will continue ingesting 50 ml of D_2O twice daily. Bilateral biopsies obtained from each leg at 1 *or* 2 weeks post-TKA will be analyzed to determine muscle protein synthesis rates. All subjects will have a total of two biopsies from each leg, in a fasting state. This will allow us to determine the independent effects of supplementation on rates of muscle protein synthesis and breakdown (2H_2O) during the acute and sub-acute period.

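### Aim 1 randomises biopsy week but no stated model uses it, and the 10 per group planned for biopsy outcomes is too few for two of the three effects the plan expects

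*Combined protocol and SAP*

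**What the plan says.** The design is a "parallel clinical trial design with 1:1 allocation ratio to EAA versus Placebo". Under Target Population and Power analyses, Aim 1 patients are further "randomized to either 1 week or 2 week post-operative biopsies". Figure 1 and its notes give each patient one biopsy occasion in the operating room and one afterwards, at week 1 or week 2. Biopsy week is therefore a between-patient factor. Target Population names gender as the stratification factor.

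Under Study Aim #1, Randomization Assignments, the plan says "This will allow us to collapse data by group treatment group" and then lists questionnaire, activity, food-log, strength, muscle-volume and functional data. The same sentence treats metabolism after surgery as measured at separate 1-week and 2-week points.

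Data Analysis names ANCOVA with the pretest measure for both aims. Random coefficients analysis is assigned to muscle, strength, mobility, accelerometer and functional data. The effect size d is defined "after adjusting x for pretest scores and covariates (sex, tourniquet time, age, body mass index, fat/carbohydrate/protein intake"). No section gives a biopsy-week term, an arm-by-week term, or a rule for combining or separating the weeks.

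Power calculations for Aim 1 begin "For a sample size of 20 completed subjects/group (10/group for metabolic studies", with 20 per arm for EAA versus placebo overall. The stated detectable effects are "ESs of $d > 1.10$ with 85% power, assuming no pretest covariate". For outcomes with a correlated baseline value, the text adds that "the minimally detectable ES drops to 0.95 or 0.72 with pretest covariates of $r = .50$ or $.75$, respectively". The paragraph notes that all preliminary cell and FSR effects exceeded .95 and concludes that 10 subjects per condition suffice.

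**The concern.** The primary biochemical outcomes all come from biopsies, and the plan does not say which patients enter that comparison or with what model. Time since surgery could well change synthesis and signalling. Heavy-water intake also stops at week 1 for half the patients and at week 2 for the rest, so the labelling period differs between the halves.

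If the weeks are analysed separately, as the 10-per-group figure implies, each test has half the patients, and the detectable effects printed beside it do not apply. If the weeks are combined without a week term, any week difference goes into the error variance. With neither route fixed, the choice among pooled, week-1 and week-2 results could be made after seeing the data.

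**Working it through.** **Inputs.** From Power analyses: "we have assumed a Type I error rate (α) of $.05$, two-tailed"; 85% power; 20 completers per arm, 10 per arm for metabolic studies; expected effects REDD1 1.24, SLC36A2 1.27, FSR 1.51.

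**Method.** Two-sample t test with n per arm: df = 2n − 2, noncentrality = d × √(n/2), power from the noncentral t. The detectable effect (MDES) is the d that gives 85% power. A pretest correlation r multiplies the MDES by about √(1 − r²).

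**Step 1: the plan's own figures.**
- At 20 per arm the MDES is 0.97, not 1.10. Power at d = 1.10 is 92.4%.
- At 10 per arm the MDES is 1.42. Power at d = 1.10 is 64.3%.
- The stated 1.10 corresponds to about 16 per arm (MDES 1.095). That would fit a 20% loss from 20, but this is an assumption, and the text says completed subjects.
- The covariate steps follow from 1.10: 1.10 × √(1 − 0.25) = 0.953 and 1.10 × √(1 − 0.5625) = 0.728, against the stated 0.95 and 0.72.

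So 1.10, and the 0.95 derived from it, belong to neither stated sample size. They are cautious for 20 per arm and too optimistic for 10.

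**Step 2: power at each sample size, no further covariate gain.**

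| Outcome | d | Noncentrality, 10/arm | Power, 10/arm | Noncentrality, 20/arm | Power, 20/arm |
|---|---|---|---|---|---|
| REDD1 | 1.24 | 2.773 | 74.6% | 3.921 | 96.9% |
| SLC36A2 | 1.27 | 2.840 | 76.6% | 4.016 | 97.5% |
| FSR | 1.51 | 3.376 | 89.1% | 4.775 | 99.6% |

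The critical t is 2.101 on 18 df and 2.024 on 38 df. REDD1 and SLC36A2 lie below 1.42 and miss 85%. The plan's average effect of 1.37 also lies below 1.42 (power 82.6%).

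**Step 3: all 40 patients with a week term.** One degree of freedom for week gives an MDES of 0.973; week plus arm-by-week gives 0.974. Power at d = 1.24 is 96.8%. The arm-by-week contrast compares two differences, each with 10 per arm. Its standard error is √(4/10) = 0.632 SD, against √(2/20) = 0.316 SD for the week-averaged effect. Its MDES is therefore about 2 × 0.974 = 1.95.

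**Step 4: all 40 patients without a week term.** With half of each arm in each week and a mean difference of s within-week SDs, the error SD is multiplied by √(1 + s²/4). The documents give no value for s, so these values are assumptions.

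| s (SD) | SD factor | MDES, 20/arm | Power at d = 1.24 |
|---|---|---|---|
| 0 | 1.000 | 0.97 | 96.9% |
| 0.5 | 1.031 | 1.00 | 96.0% |
| 1.0 | 1.118 | 1.09 | 92.7% |
| 1.5 | 1.250 | 1.22 | 86.4% |
| 2.0 | 1.414 | 1.38 | 77.1% |

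**The case against.** Three stronger readings are tempting, and the documents support none of them.

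- A reader might take the covariate list as the declared ANCOVA adjustment set and infer that the plan excludes week. The list only says how d was derived for the power calculation. The ANCOVA paragraph gives no closed list. What stands is that the model is unstated.
- A reader might take the sentence on collapsing data as a plan to pool biopsy results over weeks. The outcomes it lists do not come from the biopsy, and it goes on to separate the weeks for metabolism. Step 4 is therefore what would happen under a route the plan does not describe.
- A reader might infer that ignoring week biases the treatment comparison. Week is randomised, so leaving it out costs precision only. At d = 1.24 the cost is small unless the weeks differ by more than about 0.8 SD, where power is 94.4%.

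It is also fair to say that the 10 per group is disclosed and that separate weeks may be the question the investigators want answered. That stands. The defect is that adequacy is claimed at 10 using figures for a larger sample.

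The best defence of that claim is covariate gain. At r = .50 the 10-per-arm MDES is 1.23, with power of 85.5%, 87.1% and 95.6%, which just reaches the target. But the plan defines d as already adjusted for pretest. If that adjustment extends to the SD, applying r again counts the gain twice. The pre-post correlations it reports are for muscle volume, strength and stair descent, with none for a biopsy outcome.

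**Conclusion.** The concern holds in this form: biopsy week is a randomised factor that no stated model uses, and the plan's own sizing for biopsy outcomes leaves 10 per arm. At that size the 85% MDES is 1.42, and the claim of sufficiency fails for REDD1 (75%) and SLC36A2 (77%) while holding for FSR (89%). Keeping all 40 patients with a week term brings the MDES to about 0.97.

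This assumes a two-sided .05 test, 10 completers per arm in each week, the plan's effect sizes taken at face value, and no covariate gain beyond what those effect sizes contain. The 0.97 applies to a week-averaged effect of the expected size; a treatment effect confined to one week would be diluted in it. The loss from pooling without a week term cannot be sized from the documents, because they give no week difference.

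**What to change.** For all Aim 1 biopsy outcomes, state one ANCOVA on all 40 patients with arm, biopsy week (1 versus 2), sex (the stratification factor) and baseline. Name the week-averaged arm effect as the main contrast. Report arm-by-week and the two week-specific arm effects as secondary, and do not read a non-significant interaction as evidence that the weeks agree. If the investigators regard a week-specific effect as the main question, they should say so and accept the power at 10 per arm.

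Restate the power paragraph at the sample size each contrast uses: 0.97 at 20 per arm and 1.42 at 10 per arm, before covariate gain. Any correlation applied on top should be one observed for a biopsy outcome, with a statement of whether d is already adjusted for it.

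The cost is one or two degrees of freedom for the week terms and no new data. There is also a cost in standing. The Aim #2 website text says the first part was completed in 2016, and the section on benefits to participants reports muscle-loss results from 39 patients in 2014-2016. The documents do not say whether the biopsy analyses are finished. The model should be labelled as specified after data collection, and any biopsy analysis already run should be reported beside it.
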